5.4.3 Laboratory Evaluations

Continuous laboratory parameters (serum chemistry, hematology), urinalysis, urinalysis [microscopic] listed in Table 4; glucose, and HbA1c will be summarized using descriptive statistics for the observed value and the change from baseline for all post-baseline study visits. Missing values for any of the laboratory evaluations will not be imputed; that is, only observed case data will be used. Categorical urinalysis data will be listed, but will not be summarized.

Table 4: Clinical Laboratory Parameters (Safety)

Hematology	Blood Chemistry (serum, fasting)

 • Hematology • Hematocrit (Hct) • Hemoglobin (Hgb) • Mean corpuscular hemoglobin (MCH) • Mean corpuscular hemoglobin concentration (MCHC) • Mean corpuscular volume (MCV) • Platelet count • Red blood (RBC) cell count • White blood (WBC) cell count with differential (absolute and %) 	
 • Albumin (Alb) • Alkaline phosphatase (Alk-P) • Alanine aminotransferase (ALT; SGPT) • Aspartate aminotransferase (AST; SGOT) • Blood urea nitrogen (BUN) • Calcium (Ca) • Carbon dioxide (CO₂) • Chloride (Cl) • Creatinine • Creatine kinase (CK) • Glucose • Lactate dehydrogenase (LDH) • Phosphorus • Potassium (K) • Sodium (Na) • Total and direct bilirubin (TB) • Total protein • Uric acid
Urinalysis (Dipstick)	Coagulation (only in patients receiving anticoagulant therapy that in the investigator's judgment require monitoring at Visit T1 and 3 to 5 days post Visit T1) 
 • Prothrombin time (PT) • International normalized ration (INR)
Urinalysis (Microscopic)-only if urine dipstick abnormal	Additional samples 
 • Hemoglobin A1C (HbA1C) • PK

The number and percentage of patients with laboratory abnormalities (i.e., laboratory values outside the stated laboratory normal range) will be summarized at each time point (i.e., including baseline and post-baseline time points) for each laboratory parameter. The determination of laboratory abnormalities will take into account any unscheduled

laboratory assessments. Additional lab-related summaries will be provided as follows for hepatic safety, musculoskeletal safety, diabetes and hyperglycemia, and renal safety.

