**Safety and Monitoring:**

Post-randomization, lipid results will be masked in order to maintain the blind.

Monitoring and Management of Potential AEs and Adverse Events of Special Interest (AESI)

Adverse Events Associated with Experience with bempedoic acid to date:

Potential AEs:

Based on findings in nonclinical models, potential AEs include reversible hypoglycemia and metabolic acidosis. Potential cases of reversible hypoglycemia and metabolic acidosis will be identified by routine safety monitoring of AEs and clinical safety laboratories.

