### 7.2. Subject Exclusion Criteria

Patients who meet any of the following criteria will not be randomized:

1. Homozygous Familial Hypercholesterolemia (HoFH)

2. Total fasting TG  $\geq 500$  mg/dL (5.6 mmol/L) at Month -3 (Visit S2)

Note: A single repeat of TG may be completed prior to initiation of the single-blind Run-in period. For those patients who have a repeat TG, the average of the 2 values will be used to determine eligibility.

3. Renal dysfunction or a glomerulonephropathy defined as either nephritic or nephrotic syndrome, including estimated glomerular filtration rate (eGFR; using central laboratory determined Modification of Diet in Renal Disease [MDRD] formula)  $<30$  mL/min/1.73 m^2 at Month -4.5 (Visit S1)

Note: A single repeat of eGFR may be completed prior to randomization. For those patients who have a repeat eGFR, the average of the 2 values be used to determine eligibility.

4. All patients with known cardiovascular disease (CVD) or peripheral arterial disease (PAD) or cerebrovascular disease (CD)

5. History of type 1 or type 2 diabetes or laboratory evidence of diabetes (fasting blood glucose [FBG]  $\geq 126$  mg/dL or glycosylated hemoglobin, Type A1C (HbA1C)  $>6.5\%$ ) without prior diagnosis of diabetes at Month -4.5 (Visit S1)

6. Uncontrolled hypertension defined as sitting systolic blood pressure (SBP)  $>160$  mmHg or diastolic blood pressure (DBP)  $>100$  mmHg at Month -4.5 (Visit S1)

7. Uncontrolled hypothyroidism, including thyroid-stimulating hormone (TSH)  $>1.5 \times$  the upper limit of normal (ULN) at Month -4.5 (Visit S1)

8. Liver disease or dysfunction, including:

a. Alanine aminotransferase (ALT) and/or aspartate aminotransferase (AST)  $\geq 2.0 \times$  ULN at Month -4.5 (Visit S1).

b. Positive serology for hepatitis B surface antigen (HBsAg) and/or hepatitis C antibodies (HCV-ABVivi) at Month -4.5 (Visit S1).

Note: If total bilirubin (TB)  $\geq 1.2 \times$  ULN, a reflex indirect (unconjugated) bilirubin will be obtained and if consistent with Gilbert's disease, the patient may be enrolled in the study.

Note: At the discretion of the investigator, a single repeat of ALT and/or AST may be completed. For those patients who have a repeat ALT and/or AST, the average of the 2 values will be used to determine eligibility. Also, if test for hepatitis C antibody is positive, but reflexive test for Hepatitis C ribonucleic acid (RNA) is negative, patient can be enrolled.

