#### **12.1.3. Reporting for Adverse Events**

All AEs occurring during the course of the study (starting from signing informed consent through 30 days after last dose of study treatment) will be collected on the AE eCRF. Patients should be instructed to report any AE that they experience to the investigator. Investigators should make an assessment for AEs at each visit and record the event on the appropriate AE eCRF.

Wherever possible, a specific disease or syndrome rather than individual associated signs and symptoms should be identified by the investigator and recorded on the eCRF. A cluster of signs and symptoms that results from a single cause should be reported as a single AE (eg, fever, elevated white blood cells [WBC], cough, abnormal chest x-ray, etc, can all be reported as “pneumonia” if that is the final diagnosis). However, if an observed or reported sign or symptom is not considered a component of a specific disease or syndrome by the investigator, it should be recorded as a separate AE on the eCRF. Additionally, the condition that led to a medical or surgical procedure should be recorded as the AE, not the procedure itself.

Any medical condition already present at screening or baseline should not be reported as an AE unless the medical condition or signs or symptoms present at baseline worsens in severity or seriousness at any time during the study. In this case, it should be reported as an AE.

Clinically significant abnormal laboratory or other examination findings that are detected during the study or are present at baseline and significantly worsen during the study should be reported as AEs, as described below. The investigator will exercise his or her medical and scientific judgment in deciding whether an abnormal laboratory finding or other abnormal assessment is clinically significant. Significant abnormal laboratory values occurring during the clinical study will be followed until repeat tests return to normal, stabilize, or are no longer clinically significant. Any abnormal test that is determined to be an error does not require reporting as an AE.

An abnormal laboratory value that is not already associated with an AE is to be recorded as an AE only if any one of the following criteria is met:

- an action on the study drug is made as a result of the abnormality
- intervention for management of the abnormality is required
- at the discretion of the investigator should the abnormality be deemed clinically significant

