5.1 General Statistical Considerations

Summary statistics for continuous variables will include the number of patients, mean, median, standard deviation or standard error, minimum, and maximum. Minimum and maximum will be presented same number of decimal places as reported/collected, one additional decimal place for mean and median, and two additional decimal places for SD.

For categorical variables, the frequency and percentage will be given. Percentage will be presented with one decimal place. All categories will be presented (even if no patients are counted in the category). Counts of zero in any category will be presented without percentage.

Data will be presented on listings in order of patient, assessment date and assessment (in order collected on CRF, unless specified otherwise). Dates will be presented in format DDMMYY YYYY.

The visit schedules and window are shown below.

Visit	S1	S2	S3	S4	T1	T2	T3, EOS
Slotted Study Month	Month -4.5	Month -3	Month -2	Month -1	Week 0	Month 1	Month 2
Target Study Day	NA	Day of first 420mg PCSK9i injection	Day of 420mg PCSK9i injection during S3	Day of 420mg PCSK9i injection during S4	Day 1	Day 31	Day 61
Analysis Visit Windows	NA	within 21 days prior to 420mg PCSK9i injection	420mg PCSK9i injection during S3 visit \pm 3 days	420mg PCSK9i injection during S4 visit \pm 3 days	PCSK9i injection (regardless dose) during T1 visit \pm 3 days	T1 injection of PCSK9i (regardless dose) + 30 \pm 3 days	T2 injection of PCSK9i (regardless dose) + 30 \pm 3 days
Protocol Defined Visit Window	-135	-90 \pm 3	-60 \pm 3	-30 \pm 3	1	31 \pm 3	61 \pm 3

The details of visit window derivations will be described on the programming specifications.

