5.4.2 Adverse Events of Special Interest

Across clinical studies to date, the most frequently reported TEAEs associated with the experiences with ETC-1002 included musculoskeletal and connective tissue disorders (pain in extremity, myalgia, arthralgia, and muscle spasms), nervous system disorders (headache), and gastrointestinal disorders (nausea and diarrhea).

As with other lipid lowering medications, adverse events of special interest (AESI) include hepatic disorders (including changes in hepatic aminotransferases), musculoskeletal events (AE and CK evaluation), new onset diabetes/hyperglycemia, renal events, and neurocognitive/neurologic events. These events will be evaluated from the AE database by SOC and PT, and will be identified as safety monitoring endpoints.

- AEs of muscle-related symptoms will be summarized by treatment group. In addition, the number and percent of patients with abnormal CK values will be summarized.
- New onset diabetes/hyperglycemia will be recorded as AEs and will be summarized using the appropriate SOC. The events will be summarized by severity and relationship to study drug for each treatment group.
- Baseline eGFR and values of CK will be summarized by treatment group and by baseline eGFR categories. Shift tables of eGFR category from baseline over the study, will be provided by treatment group.
- Neurocognitive events will be identified and evaluated by routine monitoring of PE findings and AEs. Summarization of neurocognitive events will occur using pre-specified MedDRA terms and will be performed by treatment group.
- Hypoglycemia/Metabolic acidosis occurrences will be summarized based on AE evaluations.

AESI will be presented in a listing and summarized by SOC, PT and treatment group.

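### SAP 5.4.3 counts glucose only as out of range, pooling low and high values, and never specifies the diabetes laboratory summary it announces

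*SAP*

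**What the plan says.** **Patient-level laboratory count.** SAP 5.4.3 states: "The number and percentage of patients with laboratory abnormalities (i.e., laboratory values outside the stated laboratory normal range) will be summarized at each time point". The count is made for each parameter, at baseline and after baseline, and takes unscheduled tests into account. No direction and no glucose or HbA1c threshold is given.

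**Continuous summaries.** The same section says that "glucose, and HbA1c will be summarized using descriptive statistics for the observed value and the change from baseline for all post-baseline study visits". SAP 5.1 defines the content: "Summary statistics for continuous variables will include the number of patients, mean, median, standard deviation or standard error, minimum, and maximum".

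**Announced summaries.** SAP 5.4.3 ends with: "Additional lab-related summaries will be provided as follows for hepatic safety, musculoskeletal safety, diabetes and hyperglycemia, and renal safety". What follows is 5.4.3.1 (hepatic), 5.4.3.2 (renal) and then 5.4.4 (physical examinations).

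**Source of the glucose harms.** SAP 5.4.2 evaluates events of special interest from the AE database. On diabetes: "New onset diabetes/hyperglycemia will be recorded as AEs and will be summarized using the appropriate SOC". Hypoglycaemia is likewise summarised from AE evaluations. The protocol synopsis (Safety and Monitoring) names a wider source: "Potential cases of reversible hypoglycemia and metabolic acidosis will be identified by routine safety monitoring of AEs and clinical safety laboratories".

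**When a laboratory value becomes an AE.** Protocol 12.1.3: "An abnormal laboratory value that is not already associated with an AE is to be recorded as an AE only if any one of the" listed criteria is met. The criteria are an action on study drug, an intervention, or the investigator's judgement of clinical significance.

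**Laboratory definition of diabetes.** Exclusion criterion 5 has one, based on fasting blood glucose (FBG) or HbA1c, and applies it at Visit S1 only.

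**The concern.** Glucose has named harms on both sides of the normal range, so direction matters more for it than for most parameters. A single out-of-range count cannot tell a reader whether an arm has more low values, more high values, or a trade between them. It also does not show which patients moved out of range after starting study drug.

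The AE route does not fully close the gap. An asymptomatic low glucose, or a new value in the protocol's own diabetic range, enters the AE data only if someone acts on it or judges it clinically significant. The laboratory summary that could have caught it is announced without content. If its criterion is chosen later, it will not have been prespecified.

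At stake is how clearly the safety tables describe two effects that the sponsor itself lists. The primary efficacy result is not affected.

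**Working it through.** The plan gives no figure on this point to reproduce. The check has a textual part and an illustrative part.

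**1. Where each glucose finding can be counted**

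| Finding after Day 1 | AE tables (SAP 5.4.2) | Out-of-range count (5.4.3) | Continuous summary (5.4.3, 5.1) |
|---|---|---|---|
| Low glucose, no AE recorded | Not counted | Counted, pooled with high | Affects mean; visible as minimum if the most extreme |
| High glucose, no AE recorded | Not counted | Counted, pooled with low | Affects mean; visible as maximum if the most extreme |
| Newly meets FBG or HbA1c evidence of diabetes, no AE recorded | Not counted | Counted as out of range if outside the laboratory's limits, not as diabetes | As above |

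No specified table gives the number of patients with low glucose, or the number who newly meet a laboratory definition of diabetes. The subsection numbers run from 5.4.3.2 straight to 5.4.4, so the announced diabetes subsection has not merely been blacked out.

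**2. What pooling can and cannot hide (hypothetical counts, 26 per arm)**

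- Active 4 low + 1 high; placebo 1 low + 4 high. Pooled: 5/26 = 19.2% against 5/26 = 19.2%. Split: 4 against 1 low, and 1 against 4 high.
- Active 4 low + 4 high; placebo 1 low + 1 high. Pooled: 8/26 = 30.8% against 2/26 = 7.7%. The difference shows.

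Pooling masks a difference between arms only when low and high values differ in opposite directions.

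**3. Does the pooled count move in a predictable direction?**

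Assumptions, none of them in the documents: normal range 70–99 mg/dL (limits 69.5 and 99.5 for rounding); fasting glucose normally distributed with mean m and SD s; a uniform drug shift d. Then

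- P(low) = Φ((69.5 − m)/s)
- P(high) = 1 − Φ((99.5 − m)/s)
- pooled = P(low) + P(high)

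With m = 95, s = 10, d = −10:

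- Before: Φ(−2.55) = 0.0054 and 1 − Φ(0.45) = 0.3264; pooled 0.3317, or 8.6 of 26.
- After (mean 85): Φ(−1.55) = 0.0606 and 1 − Φ(1.45) = 0.0735; pooled 0.1341, or 3.5 of 26.
- Low values rise from 0.1 to 1.6 of 26 while the pooled count falls.

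Pooled percentage at s = 10 for other assumed means:

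| m (mg/dL) | before | d = −5 | d = −10 |
|---|---|---|---|
| 98 | 44.3 | 26.7 | 15.7 |
| 95 | 33.2 | 19.1 | 13.4 |
| 92 | 23.9 | 14.6 | 14.6 |
| 90 | 19.1 | 13.4 | 17.2 |
| 88 | 15.7 | 13.8 | 21.3 |
| 85 | 13.4 | 17.2 | 29.8 |

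With s at 8, 10 or 12 and d at −5 or −10, the pooled count falls in all 18 combinations at m = 92, 95 and 98, by 7.5 to 34.0 percentage points. At m = 88 it falls for d = −5 and rises for d = −10. At m = 85 it rises throughout. Low values rise in every case. The sign of the pooled change therefore depends on a mean that the documents do not give.

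**4. How many diabetes cases a laboratory count could show**

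P(at least one of 26) = 1 − (1 − p)^26. For assumed p of 1%, 2%, 5% and 10% this is 23%, 41%, 74% and 94%. If none is seen, the one-sided 95% upper limit is 1 − 0.05^(1/26) = 10.9%. Any such table will hold small numbers.

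**The case against.** The strongest case against is that the gap is narrow.

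- **Layout.** SAP 5.4.3 defines an abnormality and is silent on table layout, so a split into low and high would be compatible with it. That is true, but nothing requires the split.
- **Continuous summaries.** A uniform fall in glucose, as in step 3, would show in the planned change from baseline, and the minimum and maximum show extremes on each side. This stands as partial mitigation. These statistics do not say how many patients are affected.
- **Active AE ascertainment.** Protocol 11.1.5.5 requires patient education, reminders at visits, and an AE record for every hypoglycaemia that the investigator confirms. Protocol 11.1.5.4 has the investigator assess each out-of-range value, and 13.7 says new-onset diabetes will be recorded as an AE. These steps make silent cases less likely. They still start from symptoms or rest on judgement.
- **Baseline.** The count is also given at baseline, so group rates before treatment are visible. Only the individual patient's shift is missing.

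A reader might infer more than the documents support:

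- *That low and high values cancel.* They do not: every out-of-range patient adds one to the count. Masking arises only in the comparison of arms, and only in the pattern shown in step 2.
- *That the table would point the wrong way, with fewer abnormalities on active drug.* Step 3 shows the opposite at lower assumed means. The entry ceiling on glucose does not establish that most out-of-range values will be mildly high.
- *That the plan has no laboratory view of glucose.* It has the continuous summaries, and it announces a diabetes summary. The fault is that the summary is left undefined.

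**Conclusion.** The point holds as a minor one, to consider. Three facts rest on the text alone: the out-of-range count has no direction; the specified rules for hypoglycaemia and new-onset diabetes draw on AE records, although the protocol says hypoglycaemia will be identified from laboratories too; and the announced diabetes and hyperglycaemia laboratory summary has no content.

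The consequence is possible rather than certain. A rise in low values can be masked by a fall in high values in the same arm, and a new laboratory-defined case of diabetes can be missing from every diabetes count. No general magnitude is claimed, because the illustration turns on an assumed mean, SD, normal range and drug shift. Safety analysis is descriptive, with 26 patients per arm and two months of treatment, which limits how much any of these tables can show.

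**What to change.** 1. In SAP 5.4.3, report glucose below and above the normal range separately by arm, as shifts from baseline to the lowest and to the highest post-baseline value.
2. Add the announced diabetes and hyperglycaemia subsection. By arm, give the number and percentage of patients who do not meet the protocol's laboratory evidence of diabetes (FBG or HbA1c) at Day 1 and meet it at T2 or T3, whether or not an AE was reported. HbA1c can contribute at T3 only, its one scheduled post-baseline visit.
3. Before step 2, the sponsor must reconcile the FBG cut-off in exclusion criterion 5: the synopsis has >126 mg/dL and section 7.2 has ≥126 mg/dL. This review does not say which is right.

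Cost: SAP wording and one or two descriptive tables from glucose (T1, T2, T3) and HbA1c (T1, T3) already scheduled. No new samples or visits are needed. The downside is more tables with small counts, which should be read as description only.

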5.4.3.1 Hepatic Safety

For liver-associated enzymes and total bilirubin (TB), the number and percent of patients with abnormal values for ALT ($> 3 \times \text{ULN}$, $> 5 \times \text{ULN}$), AST ($> 3 \times \text{ULN}$, $> 5 \times \text{ULN}$), and TB ($> 2 \times \text{ULN}$) will be summarized by treatment group and overall, normal baseline ALT/AST/TB and abnormal baseline ALT/AST/TB.

Potential Hy's law criteria ($> 3 \times$ upper limit of normal [ULN] for either ALT or AST, with accompanying TB $> 2 \times \text{ULN}$, with no other known cause) will also be applied to the data; any potential Hy's law cases will be listed separately.

5.4.3.2 Renal Safety

Baseline eGFR and values of CK will be summarized by treatment group and by baseline eGFR categories. Shift tables of eGFR category from baseline over the study, will be provided by treatment group.

5.4.4 Physical Examinations (PEs)

Listings of PE data will include only those records where the body system at the baseline PE was normal, but the body system at a post-baseline PE was marked as 'Change from previous exam, clinically significant.' Only changes from baseline physical examination findings that meet the definition of an AE will be recorded on the AE page of the eCRF and will be summarized with other AE outcomes.

5.4.5 Vital Signs

Actual values and changes from baseline in vital signs (heart rate, systolic blood pressure, diastolic blood pressure, weight, height [baseline only], and BMI) will be summarized using descriptive statistics by treatment group and post-baseline time point on the observed values. Baseline is defined as the last value prior to the first dose of study medication.

Vital signs data will be listed for each patient, with increases from baseline of $> 15 \text{ mmHg}$ in systolic or diastolic blood pressure flagged.

For vital signs, observed values and changes from baseline will be summarized for all post-baseline study visits.

6 Changes in Statistical Analysis Plan Based on the Study-Specific Protocol

1. To be consistent with other Esperion studies, the LDL-M will be used as primary endpoint where triglycerides (TG) > 400 mg/dL or LDL-C < 50 mg/dL for primary efficacy endpoint analysis.
2. The treatment completer set will be used for sensitivity analyses of primary and secondary efficacy endpoints.
3. AEs during run-in period will be summarized.

7 Reference

2. World Health Organization (WHO) Fact Sheet No 317 Updated January 2015.

8 Appendices

Appendix 1: Schedule of Events (Subject Visit Schedule)

Visit	Schedule of Events						
	S1 ^{1,2}	S2	S3	S4	T1	T2	T3/EOS ³
Month	Month -4.5	Month -3	Month -2	Month -1	Week 0	Month 1	Month 2
Day	Day -135	Day -90 ±3	Day -60 ±3	Day -30 ±3	Day 1*	Day 31 ±3	Day 61 ±3
Procedure							
Informed Consent	X						
Enrollment Criteria	X	X	X	X			
Demographics	X						
Medical History	X						
Concomitant Medications	X	X	X	X	X	X	X
Adverse Event Recording		X	X	X	X	X	X
Physical Exam		X					X
Weight ⁴	X				X		X
Height	X						
Vital Signs ⁶	X	X	X	X	X	X	X
Serology ⁷	X						
Serum Pregnancy/FSH ⁸	X						
Urine pregnancy test for women of childbearing potential only					X		

	Schedule of Events							
	Visit	S1 ^{1,2}	S2	S3	S4	T1	T2	T3/EOS ³
Month	Month -4.5	Month -3	Month -2	Month -1	Week 0	Month 1	Month 2	
Procedure	Day	Day -135	Day -90 ±3	Day -60 ±3	Day -30 ±3	Day 1*	Day 31 ±3	Day 61 ±3
TSH		X						
Clinical Safety Labs ⁹		X				X	X	X
Basic Fasting Lipids ¹⁰	X	X**	X	X***	X	X	X	
ApoB and hs-CRP		X				X	X	X
HbA _{1C}	X					X		X
PK – predose trough						X	X	X
Diet and exercise counseling ¹¹	X	X				X	X	X
Establish Patient Eligibility						X		
Randomization						X		
IWRS Contact ¹²	X					X	X	X
PCSK9i administered at site		X	X	X		X	X	
Double-blind Drug Dispensing						X	X	
IMP Return/Compliance							X	X
PCSK9i Return/Accountability		X	X	X		X	X	

NOTE: For patients who withdraw from study drug treatment, but consent to be followed for safety assessments and return to clinic for these visit, the visits will occur according to the protocol schedule. Safety assessments should include clinical safety and basic lipid laboratories, adverse events (AEs), physical examination (PE), vital signs. For patients who withdraw from study drug treatment, but consent to be followed for safety assessments by phone, the telephone contacts will occur according the protocol schedule with information regarding current health status and to collect information on AEs (eg, recent procedures, hospitalizations, and if the patient has died, the cause of death). If a patient does not provide consent to be followed for

safety assessments per the protocol (either by returning to clinic or by phone), Visit T4 will be considered the End of Study (EOS)/Early Withdrawal from study and no further visits will be scheduled.

¹ An optional basic fasting lipid MAY be completed prior to S2, but must occur just prior to the next witnessed PCSK9i dose if patient fails to meet lipid entry criterion at Visit S1. If this optional basic fasting lipid is completed, the average of the 2 lipid values will be used to determine eligibility.

² A recheck of blood pressure may be completed prior to T1 if the patient's diastolic blood pressure (DBP) and/or systolic blood pressure (SBP) meet the exclusion criteria levels. Patients may randomize after blood pressure medications have been adjusted, the patients have been on stable doses of blood pressure medications for at least 2 weeks, and the repeat blood pressure values (DBP and/or SBP) do not meet exclusionary values. Repeat labs may be completed prior to T1 to determine eligibility if the patient's estimated glomerular filtration rate (eGFR), alanine aminotransferase (ALT), aspartate aminotransferase (AST) or other labs meet exclusion criteria levels. If this optional lab is completed, the repeated value will be used to determine eligibility.

³ All procedures will be completed for all patients at either EOS if completing the study or early withdrawal.

⁴ Body weight will be measured while fasting, using consistent scales, after voiding, and without shoes and outerwear (eg, coats).

⁶ Vital signs will include DBP, SBP, heart rate (HR) and will be collected prior to any blood sample collection. Patient will rest for 5 minutes prior to assessments

⁷ Serology for HBsAg, HCV-ABV

⁸ Pregnancy test completed in women of child-bearing age only. FSH in naturally postmenopausal women ≥ 1 year without menses and < 55 years;

⁹ Clinical safety labs include hematology, blood chemistry, and urinalysis at all visits. Please refer to laboratory manual for detailed schedule of tests.

¹⁰ Basic fasting lipids include total cholesterol (TC), calculated low-density lipoprotein cholesterol (LDL-C), [REDACTED] non-HDL-C, and [REDACTED].

¹¹ Diet and exercise counseling per local and/or regional guidelines for the management of hyperlipidemia.

¹² Interactive web response system (IWRS) contact at either an early withdrawal or an EOS visit to register study discontinuation visit date.

*Patients must be on PCSK9 for 30 ± 3 days during each month of the PCSK9 run-in period before initiating Day 1.

** LDL-C must be ≥ 160 mg/dL and TG < 500 mg/dL before initiating PCSK9i. A local lab may be used to assess LDL-C and TG for eligibility prior to initiating Repatha, but a central lab must also be conducted at this visit.

*** LDL-C must be ≥ 70 mg/dL to qualify for randomization. Only a central lab may be used to assess entry LDL-C.
